Section 4, Section 6.11	
 Added “Time to loss of EASI-75 in the subset of patients who were re-randomized and achieved EASI-75 at Week 16 (EASI-75 calculated relative to baseline EASI score)” Updated “Time to loss of EASI-50 in the subset of patients who were re-randomized and achieved EASI-75 at Week 16 (EASI-50 and EASI-75 calculated relative to baseline EASI score)” to “Time to loss of EASI-50 in the subset of patients who were re-randomized at Week 16 (EASI-50 calculated relative to baseline EASI score)” Added “Percentage change in EASI score from Baseline at Week 52 in the subset of patients who were re-randomized at Week 16 ” as a major secondary endpoint for EMA Moved “Percentage change in SCORAD (having achieved EASI-75 at Week 16) from baseline at Week 52” from major secondary endpoints to other secondary endpoints 	
Added to allow analysis on time to loss of EASI-75
 
Modified to allow analysis on time to loss of EASI-50 on patients who were re-randomized at Week 16 as an overall evaluation of how soon those patients will move to escape arm
 
To reflect the change in the strategy of multiplicity control for EMA

Section 6.3	
 Added specification of covariates to be adjusted for maintenance period analysis 	Clarification
Section 6.8	
 Patient demographic variables and baseline characteristics will be summarized by treatment group for the mITT Population, the Modified Maintenance Primary Population and the Modified Maintenance W16 Escape Population. 	Added to allow the comparison between responders and non-responders at Week 16 in terms of patient characteristics

	
 The number and percentage of patients with specific medical history events of interest pre-specified on the History Assessment eCRF (hand dermatitis, facial dermatitis, conjunctivitis, herpes Zoster, and others) will be summarized for the mITT Population, the Modified Maintenance Primary Population and the Modified Maintenance W16 Escape Population by treatment group and by treatment and age groups. 	

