
Other Secondary Endpoints Specific for Maintenance Period:
 
 Percentage of patients from those re-randomized having achieved EASI-75 at Week 16 who continue to exhibit EASI-75 at Week 52 (EASI-75 calculated relative to baseline EASI score) Percentage of patients from those re-randomized having achieved IGA 0 or 1 and a ≥ 2-point improvement from Baseline at Week 16 who continue to exhibit an IGA 0 or 1 and a ≥ 2-point improvement from Baseline at Week 52 Time to loss of EASI-50 in the subset of patients who were re-randomized at Week 16 (EASI-50 calculated relative to baseline EASI score) Time to loss of EASI-75 in the subset of patients who were re-randomized and achieved EASI-75 at Week 16 (EASI-75 calculated relative to baseline EASI score) Time to loss of IGA response, ie, developing an IGA score ≥ 2 with 2 points deterioration of achieved IGA response at Week 16, in the subset of patients who were re-randomized and achieved IGA 0 or 1 and a ≥ 2-point improvement from Baseline at Week 16 	
Major Secondary Endpoints Specific for Maintenance Period:
 
 Percentage of patients from those re-randomized having achieved EASI-75 at Week 16 who continue to exhibit EASI-75 at Week 52 (EASI-75 calculated relative to baseline EASI score) Percentage of patients from those re-randomized having achieved IGA 0 or 1 and a ≥ 2-point improvement from Baseline at Week 16 who continue to exhibit an IGA 0 or 1 and a ≥ 2-point improvement from Baseline at Week 52 Percentage of patients from those with a Pruritus NRS of ≥ 4-points at baseline re-randomized having achieved ≥ 4-point reduction from baseline at Week 16 who continue to exhibit ≥ 4-point reduction from baseline at Week 52 Percentage change in EASI score from Baseline at Week 52 in the subset of patients who were re-randomized at Week 16 
Other Secondary Endpoints Specific for Maintenance Period:
 
 Percentage change in SCORAD (having achieved EASI-75 at Week 16) from baseline at Week 52 Percentage of patients from those with a Pruritus NRS of ≥ 5-points at baseline re-randomized having achieved ≥ 4-point reduction from baseline at Week 16 who continue to exhibit ≥ 4-point reduction from baseline at Week 52 Time to loss of EASI-50 in the subset of patients who were re-randomized at Week 16 (EASI-50 calculated relative to baseline EASI score) Time to loss of EASI-75 in the subset of patients who were re-randomized and achieved EASI-75 at Week 16 (EASI-75 calculated relative to baseline EASI score) Time to loss of IGA response, ie, developing an IGA score ≥ 2 with 2 points deterioration of achieved IGA response at Week 16, in the subset of patients who were re-randomized and achieved IGA 0 or 1 and a ≥ 2-point improvement from Baseline at Week 16

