6.1.3. General Considerations for Analyses During Maintenance Period

Maintenance Period starts at the first injection of study treatment at Week 16 and ends on the date of Week 52 or the ETV (between Weeks 16 and 52) unless specified otherwise.

For the efficacy and health outcome analyses, baseline is defined as the last available value before the first injection in Induction Period and, in most cases, will be the value recorded at Baseline Visit (Day 1).

Unless otherwise specified, efficacy and health outcome scores at Week 16 prior to entering Maintenance Period will be presented for the visit wise reports for Maintenance Period.

Unless specified otherwise, for the safety analyses during Maintenance Period, baseline is defined as the last available value before first injection in Maintenance Period. In most cases, this will be the measure recorded at Week 16. For TEAEs, baseline is the events ongoing just prior to the first injection of the study drug injection at Week 16.

For patients in the Modified Maintenance Primary Population, Modified Maintenance Secondary Population, Maintenance Primary Population, and Maintenance Secondary Population who met escape criteria (EASI-50 nonresponse) and escaped to lebrikizumab 250 mg Q2W at Weeks 24, 32, 40 and 48, only data in the Maintenance Blinded Period (up to the time of escape) will be included in both efficacy and safety analyses.

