6.2.2.1. Maintenance Primary Estimand (Hybrid)

The maintenance primary estimand is a hybrid estimand representing the clinical question of interest: what is the difference between treatment conditions, ie, Lebrikizumab vs Placebo, in the target patient population, in successful responses or means after 52 weeks achieved without use of systemic rescue medication, without transferring to escape arm, if topical rescue medication were not available and if all patients continued with treatment except those who discontinued due to lack of efficacy?

The maintenance primary estimand is described by the following attributes:

- Population: Modified Maintenance Primary Population as described in Section 6.1.1.
- Endpoint: apply to all major and other secondary endpoints for Maintenance Period
- How to account for intercurrent events (ICEs)
 - Subjects who require any use of systemic rescue medication, discontinue treatment due to lack of efficacy after week 16, or transfer to escape arm will be

considered as treatment failures, ie, non-responder, after the ICEs. Therefore, composite strategy is used for these types of ICEs.

- b. For subjects who require any use of topical rescue medication, a hypothetical strategy will be used to estimate what the treatment effect would have been if subjects continued with treatment. Therefore, hypothetical strategy is used for these types of ICEs.
- c. For subjects who discontinue treatment due to reasons other than lack of efficacy after week 16, a hypothetical strategy will be used to estimate what the treatment effect would have been if subjects continued with treatment. Therefore, hypothetical strategy is used for these types of ICEs.

D. Population-level summary: difference in response proportions or means between treatment conditions

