6.2.2.2. Maintenance Supportive Estimand (Hybrid)

The maintenance supportive estimand for both continuous and categorical endpoints is a hybrid estimand representing the clinical question of interest: what is the difference between treatment conditions, ie, Lebrikizumab vs Placebo, in the target patient population, in successful responses or means after 52 weeks achieved without use of systemic rescue medication, without transferring to escape arm, regardless of use of topical rescue medication and if all patients continued with treatment except those who discontinued due to lack of efficacy?

The maintenance primary estimand is described by the following attributes:

- A. Population: Modified Maintenance Primary Population as described in Section [6.1.1](#).
- B. Endpoint: apply to all major and other secondary endpoints for Maintenance Period
- C. How to account for intercurrent events (ICEs)
 - a. Subjects who require any use of systemic rescue medication, discontinue treatment due to lack of efficacy after week 16, or transfer to escape arm will be considered as treatment failures, ie, non-responder, after the ICEs. Therefore, composite strategy is used for these types of ICEs.
 - b. For subjects who require any use of topical rescue medication, observed data will be used. Therefore, treatment policy strategy is used for these types of ICEs.
 - c. For subjects who discontinue treatment due to reasons other than lack of efficacy after week 16, a hypothetical strategy will be used to estimate what the treatment effect would have been if subjects continued with treatment. Therefore, hypothetical strategy is used for these types of ICEs.

D. Population-level summary: difference in response proportions or means between treatment conditions

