6.11. Efficacy Analyses

[Table KGAC.6.11](#) includes the description and derivation of the efficacy/health outcomes measures and endpoints.

[Table KGAC.6.12](#) provides the detailed analyses relative to estimands including analysis type, method and imputation, population, time point, and treatment comparisons for efficacy/health outcomes analyses.

Table KGAC.6.11. Description and Derivation of Efficacy/Health Outcomes Measures and Endpoints

Measure	Description	Variable	Derivation / Comment	Imputation Approach if Missing Components
Investigator's Global Assessment (IGA)	The IGA is a static assessment and rates the severity of the patient's AD. The IGA is comprised of a 5-point scale ranging from 0 (clear) to 4 (severe) and a score is selected using descriptors that best describe the overall appearance of the lesions at a given time point.	IGA score	Single item. Range: 0 to 4 0 represents "clear" 4 represents "severe"	Single item, missing if missing.
		IGA [0,1] with ≥ 2 -point improvement	Observed score of 0 or 1 and change from baseline ≤ -2	Missing if baseline or observed value is missing.
		IGA [0]	Observed score of 0	Single item, missing if missing.
		Time to loss of IGA response, i.e., developing an IGA score ≥ 2 with 2 points deterioration of achieved IGA response at Week 16	Date of first time developing an increase in IGA score ≥ 2 compared to Week 16 - date of W16 re-randomization +1	If a patient has not experienced loss of IGA response by completion or early discontinuation of Maintenance Blinded Period or transfer to escape arm, the patient will be censored at the date of their last visit during Maintenance Blinded Period. If a patient has not experience loss of response by the time of systemic rescue during Maintenance Blinded Period, the patient will be censored at the date of systemic rescue.

Measure	Description	Variable	Derivation / Comment	Imputation Approach if Missing Components

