Measure	Description	Variable	Derivation / Comment	Imputation Approach if Missing Components
		Time to loss of EASI-50 Time to loss of EASI-75	Date of first time % change from baseline in EASI score >-50 - date of W16 re-randomization +1 Date of first time % change from baseline in EASI score >-75 - date of W16 re-randomization +1	If a patient has not experienced loss of EASI-50 or EASI-75 by completion or early discontinuation of Maintenance Blinded Period or transfer to escape arm, the patient will be censored at the date of their last visit during Maintenance Blinded Period. If a patient has not experience loss of response by the time of systemic rescue during Maintenance Blinded Period, the patient will be censored at the date of systemic rescue.
Body Surface Area (BSA)	The BSA assessment estimates the extent of disease or skin involvement with respect to AD and is expressed as a percentage of total body surface. BSA will be determined by the Investigator or designee using the patient palm = 1% rule	BSA score	BSA Total = BSA _{head and neck} + BSA _{trunk} + BSA _{upper extremities} + BSA _{lower extremities}	N/A – partial assessments cannot be saved.
		Change from baseline in BSA score	Change from baseline: observed BSA score – baseline BSA score	Missing if baseline or observed value is missing.
SCORing Atopic Dermatitis (SCORAD)		SCORAD score	SCORAD = A/5 + 7B/2 + C, where A is extent of disease, range 0-100 B is disease severity, range 0-18 C is subjective symptoms, range 0-20	Missing if component A or B or C is missing.
		Change from baseline in SCORAD score	Change from baseline: observed SCORAD score – baseline SCORAD score % change from baseline:	Missing if baseline or observed value is missing.
		Percent change from baseline in SCORAD score	$100 \times \frac{\text{Observed score} - \text{Baseline}}{\text{Baseline}}$	

Measure	Description	Variable	Derivation / Comment	Imputation Approach if Missing Components

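### Time to loss of IGA response censors patients who escape after losing EASI-50, so the censoring is related to prognosis; the row names no estimand and no escape-as-event analysis is planned beside it

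*SAP*

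**What the plan says.** **Event.** SAP Table KGAC.4.1 lists time to loss of IGA response as an other secondary maintenance endpoint in Week 16 IGA responders. The event requires "2 points deterioration of achieved IGA response at Week 16"; Table KGAC.6.11 derives it as the first rise of at least 2 points over Week 16.

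**Escape.** SAP 6.1.3 describes re-randomized patients "who met escape criteria (EASI-50 nonresponse) and escaped to lebrikizumab 250 mg Q2W at Weeks 24, 32, 40 and 48" and restricts their data to the blinded period up to escape.

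**Censoring.** Under Table KGAC.6.11, a patient with no recorded loss by completion, early discontinuation "or transfer to escape arm, the patient will be censored at the date of their last visit during Maintenance Blinded Period". With no loss by the time of systemic rescue, "the patient will be censored at the date of systemic rescue".

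**Method and estimand.** Table KGAC.6.12 plans Kaplan-Meier with log-rank for each regimen versus placebo and enters NA under estimand. SAP 6.1.3.1 makes the log-rank test stratified and names no effect measure.

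**Maintenance estimands.** SAP 6.2.2 recognises transfer to escape as an intercurrent event. Both hybrid estimands (6.2.2.1 and 6.2.2.2) claim to cover every major and other secondary maintenance endpoint, and both count as failures "Subjects who require any use of systemic rescue medication, discontinue treatment due to lack of efficacy after week 16, or transfer to escape arm". Their summary measure is a "difference in response proportions or means between treatment conditions".

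**The concern.** Kaplan-Meier and log-rank treat a censored patient as having the same future risk as those still under observation. Here one route to censoring is deterioration of the same disease, measured on another scale. Patients on the way to IGA loss can leave the risk set without being counted, and the curve then reads too low as a description of relapse. If this happens at different rates by arm, the contrast with placebo moves as well.

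Because the row reads NA, the plan does not say whether the curve is meant to show IGA loss as if escape did not exist or loss of control including escape. The first reading rests on an assumption that is doubtful here; the second is not what the censoring rule delivers.

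**Working it through.** **1. Event and trigger side by side.** IGA is scored at Weeks 24, 32, 40 and 48 (Protocol 7.12, 7.14, 7.16, 7.18), so a 2-point rise seen at the escape visit still counts. For a patient who has lost EASI-50 at such a visit:
- Week 16 IGA 1, now IGA 3: rise of 2, event.
- Week 16 IGA 0, now IGA 2: rise of 2, event.
- Week 16 IGA 1, now IGA 2: rise of 1, no event, censored.

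Only the third type is affected. For time to loss of EASI-50 or EASI-75, losing EASI-50 is, or implies, the event, so escape censoring does no harm there.

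**2. Arm sizes.** The plan gives no event count, power or hazard ratio for this endpoint, so there is no figure to reproduce. From SAP 5.2 and the allocation ratios: 400 × 2/3 × 0.347 = 92.5 lebrikizumab IGA responders; split 2:2:1, this is 37.0, 37.0 and 18.5.

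**3. Closed form (assumed inputs).** Let F be the Week 52 incidence of IGA loss or escape, and s the share first seen as escape without IGA loss. With proportional cause-specific hazards, the curve that censors escape shows 1 − (1 − F)^(1 − s). For F = 50% this is 46.4%, 40.5% and 29.3% at s = 10%, 25% and 50%; at s = 0 nothing changes.

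For the contrast, take F = 60% on placebo and 25% on active. The composite hazard ratio is ln(0.75)/ln(0.40) = 0.31. Censoring escape multiplies it by (1 − s active)/(1 − s placebo):
- equal shares: 0.31, but expected events fall from 37 × 0.25 + 19 × 0.60 = 20.7 to 15.5 (s = 25%) or 10.3 (s = 50%);
- 25% placebo, 0% active: 0.31/0.75 = 0.42;
- 50% placebo, 0% active: 0.31/0.50 = 0.63;
- 0% placebo, 25% active: 0.31 × 0.75 = 0.24.

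**4. Simulation (all inputs assumed).** Latent EASI, as a fraction of baseline, starts uniform on 0.05–0.25 at Week 16. Slope per 4 weeks is normal, mean 0.05 (placebo) or 0.01 (active), SD 0.05. Visit noise SD is 0.05 for EASI and 0.10 for IGA. Escape occurs at Weeks 24/32/40/48 when EASI exceeds 0.5 of baseline, and IGA loss when latent severity plus noise reaches c. About 55% of placebo and 26% of active patients escape. Week 52 IGA loss is shown as placebo / active:

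| c | Placebo escapes censored | Present rule | If nobody left | Escape as event |
|---|---|---|---|---|
| 0.4 | 2% | 73.6 / 44.7 | 74.2 / 45.1 | 74.2 / 45.1 |
| 0.5 | 16% | 59.4 / 30.9 | 64.6 / 34.2 | 65.1 / 34.6 |
| 0.6 | 48% | 36.7 / 15.8 | 54.6 / 25.3 | 58.3 / 28.1 |
| 0.7 | 79% | 14.8 / 5.1 | 45.1 / 18.3 | 55.7 / 26.1 |

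By subtraction, the placebo − active difference under the present rule is 28.9, 28.5, 20.9 and 9.7 points, against 29.1, 30.4, 29.3 and 26.8 if nobody left. Unstratified log-rank power (37 vs 19) is 63, 61, 45 and 25% under the present rule, and 64, 67, 67 and 64% with escape as an event.

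**5. The upper end is a corner case.** One threshold for everyone ignores that a Week 16 IGA 0 patient needs only IGA 2. With an assumed 30% or 50% of patients at IGA 0 (threshold 0.4) and the rest at 0.7, the share of placebo escapes censored falls from 79% to 56% or 41%. Placebo loss under the present rule becomes 34% or 46%, against 54% or 60% if nobody left.

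**The case against.** The strongest objection is that the IGA question is already answered elsewhere with escape counted against the patient. Table KGAC.6.12 analyses maintenance of IGA response in the same responders at all scheduled maintenance visits under the Maintenance Primary Estimand. Table KGAC.6.4 sets escape, systemic rescue and lack-of-efficacy discontinuation to baseline there, and Table KGAC.6.9 adds non-responder imputation. The Week 52 point is in the EMA hierarchy (SAP 6.6.2). Time to loss of EASI-50 was redefined in SAP Version 5 "as an overall evaluation of how soon those patients will move to escape arm". All of this stands and limits the consequence. It does not repair a separately reported relapse curve and test.

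A second objection is that a composite is a different endpoint. That also stands: at c = 0.7 it reads 55.7% on placebo against 45.1% for IGA loss if nobody left. This is a reason to report both, not to replace one with the other.

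A reader might go further in three ways that the documents do not support:
- *That the NA row flatly contradicts the hybrid estimands.* Their summary is proportions or means, and Table KGAC.6.12 gives another other-secondary endpoint (percentage change in SCORAD) a different estimand. It is a gap.
- *That the lebrikizumab benefit is known to be understated.* The simulations lean that way, but the closed form moves either way depending on which arm has more escapes without IGA loss.
- *That EASI-50 and EASI-75 share the fault.* Their escape censoring is harmless. Rescue and lack-of-efficacy censoring could matter in principle, but no figure supports a change.

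**Conclusion.** The point holds for time to loss of IGA response. Followed as written, the rule censors some patients because they worsened, and no planned time-to-IGA-loss analysis treats escape as an event. The size rests on the share of escapes without a 2-point IGA rise, which the documents do not give. If every escapee also has that rise there is no effect; under the mixed-threshold assumptions the placebo curve reads 34% or 46% instead of 54% or 60%. Direction by arm cannot be settled from the documents.

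No primary or multiplicity-controlled result depends on this curve. It is a cheap improvement to an other secondary endpoint, not a threat to the maintenance conclusions.

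**What to change.** In Tables KGAC.6.11 and KGAC.6.12, for time to loss of IGA response only:
- Add an analysis in which transfer to escape, systemic rescue and lack-of-efficacy discontinuation are events on that date, with censoring only at completion or discontinuation for other reasons. Label it time to loss of IGA response or treatment failure, and report it beside the present rule.
- Replace NA in each row with the estimand targeted. The present rule takes a hypothetical view of escape. The added analysis is closest to the Maintenance Supportive Estimand (Hybrid), where "For subjects who require any use of topical rescue medication, observed data will be used", because neither analysis has a topical-rescue step.
- State a time-to-event summary measure for each, for example the Week 52 Kaplan-Meier difference or a region-stratified hazard ratio.

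Escape censoring for EASI-50 and EASI-75 can stay.

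The cost is SAP wording, an event flag on dates already collected and a little programming. The downside is that the added endpoint is a composite that can exceed pure IGA loss. It would also count systemic corticosteroids given for an adverse event, since Protocol 6.1 classes these as rescue; the hybrid estimands already do so.
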